#### *Management Following the Confirmatory Imaging*

If repeat imaging does not confirm PD per iRECIST, as assessed by the Investigator, and the participant continues to be clinically stable, study treatment may continue and follow the regular imaging schedule. If PD is confirmed, participants will be discontinued from study treatment.

*Detection of Progression at Visits After Pseudo-progression Resolves*

After resolution of pseudo-progression (i.e., achievement of iSD/iPR/iCR), iUPD is indicated by any of the following events:

- Target lesions
  - Sum of diameters reaches the PD threshold ( $\geq 20\%$  and  $\geq 5$  mm increase from nadir) either for the first time, or after resolution of previous pseudo-progression. The nadir is always the smallest sum of diameters seen during the entire trial, either before or after an instance of pseudo-progression.
- Non-target lesions
  - If non-target lesions have never shown unequivocal progression, their doing so for the first time results in iUPD.
  - If non-target lesions have shown previous unequivocal progression, and this progression has not resolved, iUPD results from any significant further growth of non-target lesions, taken as a whole.
- New lesions
  - New lesions appear for the first time
  - Additional new lesions appear
  - Previously identified new target lesions show an increase of  $\geq 5$  mm in the new lesion sum of diameters, from the nadir value of that sum
  - Previously identified non-target lesions show any significant growth

If any of the events above occur, the overall response for that visit is iUPD, and the iUPD evaluation process (see Assessment at the Confirmatory Imaging above) is repeated. Progression must be confirmed before iCPD can occur.

The decision process is identical to the iUPD confirmation process for the initial PD, with one exception: if new lesions occurred at a prior instance of iUPD, and at the confirmatory imaging the burden of new lesions has increased from its smallest value (for new target lesions, the sum of diameters is  $\geq 5$  mm increased from its nadir), then iUPD cannot resolve to iSD or iPR. It will remain iUPD until either a

decrease in the new lesion burden allows resolution to iSD or iPR, or until a confirmatory factor causes iCPD.

Additional details about iRECIST are provided in the iRECIST publication.

WHO	World Health Organization
λ_z	terminal elimination rate constant

1 INTRODUCTION

Clinical Trial SNDX-275-0601 is an open-label Phase 1b/2 evaluating the combination of entinostat with pembrolizumab in patients with advanced metastatic or recurrent NSCLC, melanoma, or mismatch repair-proficient colorectal cancer. The study has 2 phases, a Dose Escalation/Confirmation Phase (Phase 1b) and an Expansion Phase (Phase 2), with the Expansion Phase utilizing a Simon 2-stage design ([Simon 1989](#)) for each cohort. An additional cohort (Entinostat Monotherapy Immune Correlate [EMIC] Cohort) evaluating single agent entinostat followed by the combination will also be evaluated in patients with NSCLC in the Phase 2 expansion phase.

This SAP contains a detailed description of the data presentations and statistical analyses that will be included in the clinical study report for Protocol SNDX-275-0601. The statistical methods and analyses described here are based on those presented in the study protocol. Any changes made to the planned analyses after this document has been finalized will be noted in the clinical study report.

This version of the SAP was written in accordance with the following protocol versions:

Table 1-1 **Protocol Versions**

Protocol	Version Date
Original	08-April-2015
Amendment #1	05-June-2015
Amendment #2	04-April-2016
Amendment #3	23-February-2017
Amendment #4	25-August-2017
Amendment #5	12-April-2018

The first patient was enrolled under the original protocol dated 08-April-2015. Since then, study 601 has undergone 5 amendments (Table 1).

For Amendment #1, significant changes include, addition of exploratory endpoint, the clarification of duration of therapy, clarification of the number of patients enrolled, modification of the language to include a definition of a DLT-evaluable patient, and the definition of DLT.

Amendment #2 clarified the process of deciding on the Recommended Phase 2 Dose (RP2D), updated the Adverse Events terms of attribution/relatedness, updated the dose modification requirements for entinostat.

Amendment #3 added an additional cohort of patients: Mismatch Repair-Proficient Colorectal Cancer and updated pembrolizumab background information

Amendment #4 increased the sample size for Cohorts 2 and 3 and modified the corresponding statistical considerations accordingly (Section 12 of the protocol), removed Proton Pump Inhibitors (PPIs) from the list of medications to be avoided, and modified Eligibility Criteria to clarify prior disease progression on immunotherapy.

Amendment #5 increased the sample size for Cohort 4 and modified the corresponding statistical considerations accordingly (Section 12 of the protocol), updated the standard language regarding pembrolizumab, clarified the description of the irRECIST process for assessment of disease progression for imaging and treatment after first radiologic evidence of progressive disease.

2 STUDY SUMMARY

2.1 STUDY OBJECTIVES

2.1.1 Primary Objectives

Phase 1b (Dose Escalation/Confirmation Cohorts): To determine the dose-limiting toxicities (DLT) and maximum tolerated dose (MTD) or recommended Phase 2 dose (RP2D) of entinostat (SNDX-275) given in combination with pembrolizumab.

Phase 2 (Expansion Cohorts): To evaluate the preliminary efficacy of entinostat at the RP2D in combination with pembrolizumab in patients with melanoma, non-small cell lung cancer (NSCLC), and mismatch repair-proficient colorectal cancer (CRC), as determined by overall response rate (ORR), per the Immune-related Response Evaluation Criteria in Solid Tumors (irRECIST) in each cohort evaluated.

2.1.2 Secondary Objectives

Efficacy: To evaluate the efficacy of entinostat in combination with pembrolizumab in patients with melanoma NSCLC, and mismatch repair-proficient colorectal cancer as determined by secondary measures of efficacy per the Response Evaluation Criteria in Solid Tumors version 1.1 (RECIST 1.1) and Immune-related Response Evaluation Criteria in Solid Tumors (irRECIST) including:

- Clinical benefit rate (CBR) (complete response [CR]+partial response [PR]+stable disease [SD]) at 6 months
- Progression-free survival (PFS) status at 6 months
- PFS
- Overall survival (OS)

In patients who experience a response to treatment (i.e., CR or PR):

- Duration of response (DOR)
- Time to response (TTR)

Safety: To evaluate safety and the tolerability of entinostat in combination with pembrolizumab, as measured by clinical adverse events (AEs) and laboratory parameter

2.1.3 Exploratory Objectives

2.2 STUDY ENDPOINTS

2.2.1 Primary Efficacy Endpoint

- ORR, as determined by irRECIST

2.2.2 Secondary Endpoints (analyzed for the same populations as the primary endpoint)

An analysis of efficacy endpoints will be performed with response determined using irRECIST, as well as RECIST version 1.1.

- CBR (i.e., CR+PR+SD at 6 months)
- PFS status at 6 months
- PFS
- OS

[figure not shown]
In patients who experience a response to treatment (i.e., CR or PR):

- DOR
- TTR

Safety:

- Determination of DLTs, MTD, and RP2D (in Phase 1 only)
- Incidence of treatment-emergent adverse events (TEAEs), serious adverse events (SAEs), AEs resulting in the permanent discontinuation of study drug, and deaths occurring within 90 days of the last dose of study drug
- Changes from baseline in laboratory, vital signs, Eastern Cooperative Oncology Group (ECOG), physical examination, and electrocardiogram (ECG) values

2.2.3 Exploratory Endpoints

[figure not shown]

2.3 STUDY DESIGN

Study SNDX-275-0601 is an open-label, Phase 1b/2 study evaluating the combination of entinostat plus pembrolizumab in patients with advanced metastatic or recurrent NSCLC, CRC, or melanoma. The study has 2 phases, a Dose Escalation/Confirmation Phase (Phase 1b) and an Expansion Phase (Phase 2), with the Expansion Phase utilizing a Simon 2-stage design ([Simon 1989](#)) for each cohort. An additional cohort (Entinostat Monotherapy Immune Correlate Cohort (EMIC)) evaluating single agent entinostat followed by the combination in patients with NSCLC will also be evaluated in the Phase 2 Expansion Phase. The study schema is presented in Figure 2-1.

Figure 2-1:

Regardless of phase, patients will be screened for study eligibility within 21 days before enrollment into the study. Patients who are determined to be eligible based on screening assessments, will be enrolled in the study within 3 days of starting study treatment on Cycle 1, Day 1 (C1D1) and will receive entinostat in combination with pembrolizumab.

A cycle is 21 days in length. During treatment, patients will attend study center visits and have study evaluations performed on C1D1, C1D8, and C1D15; D1 and D15 of C2; and on D1 of each cycle thereafter. Patients will have radiological disease assessments performed during screening and every 6 weeks (+/-3 days) (Week 6, Week 12, etc.) during treatment. The maximum duration of treatment for this study is planned to be 2 years. Disease will be assessed by computed tomography (CT), magnetic resonance imaging (MRI), and bone scans, as appropriate, and response will be assessed by the Investigator using irRECIST. Safety will be assessed during the study by documentation of AEs, clinical laboratory tests, physical examination, vital sign measurements, ECGs, and Eastern Cooperative Oncology Group (ECOG) performance

status. If a patient permanently discontinues 1 of the 2 study drugs (either entinostat or pembrolizumab), the patient may continue to receive monotherapy for up to 2 years, unless alternate therapy is started or another discontinuation criterion is met. After discontinuation of both study drugs, patients will complete an End of Treatment (EOT) visit within 7 days after the last study drug dose and Safety Follow-up visits 30 days and 90 days thereafter. After completion of the 30-day Safety Follow-up (F/U) visit, patients who have not experienced progressive disease (PD) are to be followed every 2 months until PD and every 3 months thereafter until death or closure of the study by the Sponsor. Collection of fresh tumor tissue core biopsy (image-guided if applicable) and blood samples are outlined in Section 5.1 of the protocol.

2.3.1 Number of Patients and Sample Size Considerations

Phase 1b/Safety Lead-in (Dose Determination Phase):

Three to 6 patients will be enrolled in each dose cohort based on a standard Phase 1 dose escalation scheme. Each patient will participate in only 1 dose cohort. The total number of patients to be enrolled in the Dose Escalation/Confirmation Phase is dependent upon the observed safety profile, which will determine the number of patients per dose cohort, as well as the number of dose escalations required to achieve the MTD or RP2D.

A starting sample size of at least 3 patients per dose cohort, expanding to 6 patients in the event of a marginal DLT rate (33%) was deemed to be a safe and conventional approach in the dose escalation of a novel oncologic agent. Assuming a true DLT rate of 5% or less, there would be a 3% chance that dose escalation would be halted in a given cohort (i.e., observing 2 or more patients with DLT). If a true DLT rate of 50% is assumed, then there would be an 83% chance that dose escalation would be halted in a given cohort.

A total of 9 additional patients will be enrolled in the Dose Confirmation Cohort to obtain additional AE, immune correlate, and anti-tumor activity data on entinostat at the MTD or RP2D in combination.

Phase 2/Expansion Phase:

In the Expansion Phase of the study, the safety and preliminary antitumor activity of entinostat when administered at the RP2D with pembrolizumab will be explored in up to 4 cohorts of adult solid tumors as previously defined. Up to 252 patients are planned to be enrolled among the 4 cohorts. Patients will be enrolled in each cohort according to a single-arm study design with ORR, as determined by irRECIST, as the primary endpoint. The Expansion Phase will be carried out in 2 stages so that enrollment for 1 or more of the cohorts evaluated can terminate early in the event the antitumor activity of the combination regimen is not sufficient. The decision to terminate or continue enrollment for each cohort will be made independently of the other. The number of patients evaluated in each stage and the minimum number of responders needed to continue to the next stage, as described for cohorts 1, 2 and 3, was determined based on the optimum version of Simon's 2-stage design ([Simon 1989](#)), with 80% power and 1-sided significance level of 10%. For cohort 4, the number of patients evaluated in each stage and the minimum number of responders needed to continue to the next stage was determined based on the optimum version of Simon's 2-stage design, with 90% power and 1-sided significance level of 5%.

Cohort 1 (NSCLC patients with squamous cell and adenocarcinoma histology who have not been previously treated with a PD-1 or PD-L1-blocking antibody)

A maximum of 46 patients will be enrolled in Cohort 1. A true ORR of 35% is hypothesized. An ORR greater than 20% is considered a lower threshold for antitumor activity that would warrant continued development. Based on the design elements specified above, up to 13 patients may be enrolled for either tumor type during the first stage; if 2 or fewer patients achieve an objective response (CR or PR), confirmed or unconfirmed, then enrollment will terminate; otherwise, 33 additional patients will be enrolled during the second stage. Upon completion of the second stage, if 13 or more patients out of the 46 enrolled achieve CR or PR, then the true ORR for the combination therapy likely exceeds 20%, the lower threshold of acceptable antitumor activity. Alternatively, if 12 or fewer patients achieve an objective response at the end of the second stage, then the true ORR is likely 20% or lower, and further evaluation of the

combination therapy may not be pursued for that tumor type. If the true ORR is 20% or less for a tumor type, then the expected sample size is 29.4, with probability of terminating enrollment at the end of the first stage equal to 50%.

Cohort 2 (Patients with NSCLC (any histology) who have previously been treated and progressed on a PD-1 or PD-L1-blocking antibody)

A maximum of 56 patients will be enrolled in Cohort 2. A true ORR of 15% is hypothesized. A response rate greater than 5% is considered the lower threshold for antitumor activity that would warrant continued development in this setting. Based on the design elements specified above, up to 20 patients may be enrolled during the first stage: if 1 or no patients achieve a CR or PR, confirmed or unconfirmed then enrollment will terminate; otherwise 36 additional patients will be enrolled during the second stage. Upon completion of the second stage, if 5 or more patients out of 56 enrolled achieve CR or PR, then true ORR for the combination regimen likely exceeds 5%, the lower threshold of acceptable antitumor activity. Alternatively, if 4 or fewer patients achieve an objective response at the end of the second stage, then the true ORR is likely 5% or lower and further evaluation of the combination therapy may not be pursued in this setting. If the true ORR is 5% or less, then the expected sample size is 29.5, with probability of terminating enrollment at the end of the first stage equal to 74%. However, with Amendment 5, the study design for this cohort is changed from Simon 2-stage design to single proportional binomial test after moving in to 2nd stage. Based on single proportional binomial test, maximum of 70 patients are enrolled in Cohort 2.

Ninety-six percent 1-sided confidence interval (or 92% 2-sided confidence interval) of the observed one sample proportion will be calculated. The trial will be considered a success if the lower limit of 96% confidence interval is greater than 5%.

Syndax will conduct one administrative analysis when at least 60% (42 out of 70 patients) of patient information has been accrued in cohort 2 for decision making for late phase development planning. This administrative look will not lead to stopping of the study. Nonetheless, 0.01 alpha is being allocated for the first administrative look, leaving 0.04 alpha for the final analysis.

Cohort 3 (Patients with melanoma who have previously been treated and progressed on a PD-1 or PD-L1-blocking antibody)

A maximum of 34 patients will be enrolled in Cohort 3. A true ORR of 25% is hypothesized. A response rate greater than 10% is considered the lower threshold for antitumor activity that would warrant continued development in this setting. Based on the design elements specified above, up to 13 patients may be enrolled during the first stage: if 1 or no patients achieve a CR or PR, confirmed or unconfirmed then enrollment will terminate; otherwise 21 additional patients will be enrolled during the second stage. Upon completion of the second stage, if 6 or more patients out of 34 enrolled achieve CR or PR, then true ORR for the combination regimen likely exceeds 10%, the lower threshold of acceptable antitumor activity. Alternatively, if 5 or fewer patients achieve an objective response at the end of the second stage, then the true ORR is likely 5% or lower and further evaluation of the combination therapy may not be pursued in this setting. If the true ORR is 10% or less, then the expected sample size is 20.9, with probability of terminating enrollment at the end of the first stage equal to 62%. However, with Amendment 5, the study design for this cohort is changed from Simon 2-stage design to single proportional binomial test after moving in to 2nd stage. Based on single proportional binomial test, maximum of 52 patients are enrolled in Cohort 3. Ninety-six percent 1-sided confidence interval (or 92% 2-sided confidence interval) of the observed one sample proportion will be calculated. The trial will be considered a success if the lower limit of 96% confidence interval is greater than 10%. Syndax will conduct one administrative analysis when at least 60% (31 out of 52 patients) of patient information has been accrued in cohort 3 for decision making for late phase development planning. This administrative look will not lead to stopping of the study. Nonetheless, 0.01 alpha is being allocated for the first administrative look, leaving 0.04 alpha for the final analysis.

Cohort 4 (Patients with CRC who have not previously been treated on a PD-1 or PD-L1-blocking antibody)

A maximum of 84 patients will be enrolled in Cohort 4. A true ORR of 15% is hypothesized. An ORR greater than 5% is considered the lower threshold for antitumor

activity that would warrant continued development in this setting. Based on the optimum version of Simon's 2-stage design, with 90% power and 1-sided significance level of 5%, up to 37 patients may be enrolled during the first stage: if fewer than or equal to 2 patients achieve a CR or PR, confirmed or unconfirmed, then enrollment will terminate; otherwise, 47 additional patients will be enrolled during the second stage. Upon completion of the second stage, if 8 or more patients of the 84 enrolled achieve CR or PR, then the true ORR for the combination regimen likely exceeds 5%, the lower threshold of acceptable antitumor activity. Alternatively, if 7 or fewer patients achieve an objective response at the end of the second stage, then the true ORR is likely 5% or lower and further evaluation of the combination therapy may not be pursued in this setting. If the true ORR is 5% or less, then the expected sample size is 50.2, with probability of terminating enrollment at the end of the first stage equal to 72%.

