Patients who experience a DLT will be allowed to remain on study if they meet the following criteria: (1) the Investigator believes it is appropriate for patients to remain on study; (2) the event has resolved and no longer meets the definition of DLT; and (3) the timeline for resolution falls within the guidelines for dose delays ([Section 8.4](#)).

Patients who complete C1 may continue on study as long as, in the Investigator's judgment, the patient is tolerating study treatment, is not at an increased safety risk, and continues to meet protocol eligibility criteria.

After completion of the Dose Escalation/Confirmation Phase of the study, with identification of the MTD or RP2D, the Phase 2 portion of the study will commence.

**Phase 2 (Expansion):** In the Expansion Phase, entinostat in combination will be evaluated using the RP2D identified in the Dose Escalation/Confirmation Phase. Up to 4 Expansion Cohorts consisting of distinct subsets of patients with solid tumor cancers may be explored. Each cohort evaluated during the Expansion Phase will employ a Simon 2-stage design. The final decision about which Expansion Cohorts to study will be based on data from the Dose Escalation/Confirmation Phase, emerging clinical data from other studies, and/or nonclinical data. Expansion cohorts may include:

1. Cohort 1: NSCLC, with squamous cell or adenocarcinoma histology who have not been treated with a PD-1 or PD-L1 blocking antibody

 Depending upon emerging data, the Sponsor may elect, instead of histology, to evaluate NSCLC consisting of PD-1+ and PD-L1+ NSCLC patients. In this case, the protocol will be amended accordingly.

2. Cohort 2: Patients with NSCLC (any histology) who have previously been treated with and unequivocally progressed on either a PD-1 or PD-L1-blocking antibody
3. Cohort 3: Patients with melanoma who have previously been treated with and unequivocally progressed on either a PD-1 or PD-L1-blocking antibody (i.e., pembrolizumab, nivolumab, MEDI4736, or GNE PDL1 [MPDL3280A])
4. Cohort 4: Patients with CRC (mismatch repair-proficient) who have not been previously treated with a PD-1 or PD-L1 blocking antibody

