#### 12.1.2 Expansion Phase

In the Expansion Phase of the study, the safety and preliminary antitumor activity of entinostat when administered at the RP2D with pembrolizumab will be explored in up to 4 cohorts of adult solid tumors as previously defined. Up to 252 patients are planned to be enrolled among the 4 cohorts. Patients will be enrolled in each cohort according to a single-arm study design with ORR, as determined by irRECIST, as the primary endpoint. The Expansion Phase will be carried out in 2 stages so that enrollment for 1 or more of the cohorts evaluated can terminate early in the event the antitumor activity of the combination regimen is not sufficient. The decision to terminate or continue enrollment for each cohort will be made independently of the other. The number of patients evaluated in each stage and the minimum number of responders needed to continue to the next stage, as described for cohort 1, was determined based on the optimum version of Simon's 2-stage design ([Simon 1989](#)), with 80% power and 1-sided significance level of 10%. For cohort 4, the number of patients evaluated in each stage and the minimum number of responders needed to continue to the next stage was determined based on the optimum version of Simon's

2-stage design, with 90% power and 1-sided significance level of 5%. For cohorts 2 and 3, the number of responders needed to declare the study a success was based on single proportion binomial test with 90% power and 1-sided significance level of 5%. Note that the protocol may be amended to allow for enrollment of additional or different cohorts, for example, patients with PD-L1-positive NSCLC, based on emerging data during study conduct.

Syndax will conduct one administrative analysis when at least 60% (42 out of 70 patients in cohort 2, 31 out of 52 patients in cohort 3) of patient information have accrued in cohorts 2 and 3 for decision making for late phase development planning. This administrative look will not lead to stopping of the study. Nonetheless, 0.01 alpha is being allocated to spend for the first administrative look and leaving 0.04 alpha for the final analysis.

***Cohort 1 (NSCLC patients with squamous cell and adenocarcinoma histology who have not been previously treated with a PD-1 or PD-L1-blocking antibody)***

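### SAP 2.3.1 still assigns Cohorts 2 and 3 a Simon design at one-sided 10% and 80% power, against the protocol, the SAP's own alpha split and the sample sizes it adopts

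*SAP*

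**What the plan says.** **SAP 2.3.1, opening text for the Expansion Phase.** Stage sizes and continuation counts, "as described for cohorts 1, 2 and 3, was determined based on the optimum version of Simon's 2-stage design", "with 80% power and 1-sided significance level of 10" percent. Only Cohort 4 is given 90% power and 5%.

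**Protocol 12.1.2 (and the synopsis).** The 10%/80% Simon sentence covers Cohort 1 alone. For Cohorts 2 and 3 the responder count needed for success "was based on single proportion binomial test with 90% power and 1-sided significance level of 5" percent.

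**SAP 2.3.1, cohort paragraphs.** Each opens with the Simon maximum (56 for Cohort 2, 34 for Cohort 3) and its success count: "if 5 or more patients out of 56 enrolled achieve CR or PR, then true ORR for the combination regimen likely exceeds 5" percent, and "if 6 or more patients out of 34 enrolled achieve CR or PR". Each then says that Amendment 5 replaced the Simon design with a single-proportion binomial test, sets the maximum at 70 or 52, and requires a one-sided 96% lower limit above 5% or 10%. On alpha: "0.01 alpha is being allocated for the first administrative look, leaving 0.04 alpha for the final analysis".

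**Other leftovers.**
- SAP 1 and SAP 2.3 describe the trial "with the Expansion Phase utilizing a Simon 2-stage design" for every cohort.
- Protocol 5.1 says "Each cohort evaluated during the Expansion Phase will employ a Simon 2-stage design", although its opening paragraph limits Simon to Cohorts 1 and 4.
- SAP 1 credits the new sizes and statistics for Cohorts 2 and 3 to Amendment 4; SAP 2.3.1 credits the design change to Amendment 5.

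**The concern.** These are the primary tests of two cohorts in an open-label trial, and each carries a declared success criterion. The SAP should give one level, one power and one design for each. Instead, its governing sentence gives a level twice the protocol's, a lower power and a different design, and nowhere in SAP 2.3.1 is 5% or 90% stated for Cohorts 2 and 3. Anyone who takes the design characteristics from that sentence will report the wrong ones. Because the text is inconsistent at this point, it also matters that neither document says which interval method or which responder count decides success.

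**Working it through.** **1. Inputs.** Null and target rates are 5% and 15% for Cohort 2, and 10% and 25% for Cohort 3 (both documents). N is 70 and 52. The candidate pairs are one-sided 10% with 80% power (SAP opening text), one-sided 5% with 90% (protocol), and 0.04 with 90% (the final-analysis share of the split).

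**2. Where 10%/80% belongs.** The SAP's older figures reproduce by exact enumeration.
- Cohort 2 (stop at 1 or fewer of 20; success at 5 or more of 56): early stopping under the null 0.736; expected size 20 + 36 × (1 − 0.736) = 29.5; type I error 9.7%; power 80.1%. The SAP prints 74% and 29.5.
- Cohort 3 (stop at 1 or fewer of 13; success at 6 or more of 34): early stopping 0.621; expected size 13 + 21 × (1 − 0.621) ≈ 20.95; type I error 9.6%; power 81.1%. The SAP prints 62% and 20.9.

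So 10%/80% is the basis of the replaced 56- and 34-patient designs.

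**3. What N = 70 and N = 52 correspond to.** One-sample normal approximation:

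n = [z(1−α)·√(p0(1−p0)) + z(power)·√(p1(1−p1))]² / (p1−p0)²

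- Cohort 2, α = 0.04, 90% power: (1.7507 × 0.2179 + 1.2816 × 0.3571)² / 0.10² = 0.8392² / 0.01 = 70.4
- Cohort 3, α = 0.04, 90% power: (1.7507 × 0.3000 + 1.2816 × 0.4330)² / 0.15² = 1.0801² / 0.0225 = 51.9

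| One-sided α, power | Cohort 2 | Cohort 3 |
|---|---|---|
| 0.04, 90% | 70.4 | 51.9 |
| 0.05, 90% | 66.6 | 48.8 |
| 0.10, 90% | 54.3 | 39.2 |
| 0.10, 80% | 33.6 | 24.9 |

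Only the first row matches 70 and 52. The total of 252 in the same SAP text is 46 + 70 + 52 + 84; with the old maxima it would be 46 + 56 + 34 + 84 = 220. The opening text was therefore updated for the new sizes but not for the level, power and design.

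**4. The success rule in the two documents.** Protocol 12.1.2 and SAP 2.3.1 both use a one-sided 96% lower limit above 5% (Cohort 2) or 10% (Cohort 3). SAP 3.8 reports the matching two-sided 92% interval. Under any one interval method, a given count gets the same verdict in both.

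**5. What the unnamed method decides.** One-sided 96% lower limits:

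| Count | Exact (Clopper-Pearson) | Score (Wilson) | Exact null tail | Exact power |
|---|---|---|---|---|
| 7/70 | 0.0455, fails | 0.0531, passes | 6.0% | 91.6% |
| 8/70 | 0.0556, passes | 0.0633, passes | 2.3% | 84.3% |
| 9/52 | 0.0896, fails | 0.1002, passes | 7.1% | 93.0% |
| 10/52 | 0.1041, passes | 0.1149, passes | 3.2% | 87.1% |

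The minimum is 8/70 and 10/52 with exact limits, and 7/70 and 9/52 with score limits. The score test is the form that reproduces N = 70 and 52; its p-values at 7/70 and 9/52 are 0.0275 and 0.0395.

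**The case against.** The strongest reply is that the SAP corrects itself. Its cohort paragraphs say the Simon design was replaced, set the new N, and state the protocol's success rule. On that reading the opening sentence is stale and changes no decision. This largely stands: it disposes of a conflict in the success rule. It does not make the stated level, power and design right, because the SAP never puts the correct ones in their place.

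Two stronger inferences are tempting, and the documents support neither.
- A reader might infer that 7/70 or 9/52 succeeds under the SAP at 10% and fails under the protocol at 5%. Their exact p-values, 0.060 and 0.071, do lie between those levels. But no sentence sets a 10% test at N = 70 or 52; the 10% belongs to the Simon stages with maxima of 56 and 34. Failure at 0.04 also presumes an exact or Wald limit, since score limits pass both counts.
- A reader might infer that 5/56 and 6/34 are a second live rule with type I error near 10%. They precede the statement that the design changed, and their denominators no longer apply.

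**Conclusion.** The point holds as an error in the stated level, power and design for Cohorts 2 and 3 in SAP 2.3.1, with related leftovers in SAP 1, SAP 2.3 and Protocol 5.1 and two amendment numbers for one change. It should be corrected, but it does not create two competing success criteria.

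The consequence for decisions comes from the unnamed interval method. Exact limits hold type I error to 2.3% and 3.2%, but power is 84% and 87%, short of the stated 90%. Score limits give about 92% and 93% power, with exact type I error of 6.0% and 7.1%, above both 0.04 and the overall 0.05.

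These figures assume exactly 70 and 52 patients in the analysis, a single final test, and no adjustment for the first-stage continuation requirement that the SAP says applied before the change. The match to 0.04 and 90% is inferred from the arithmetic; the documents do not show how N was calculated.

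**What to change.** In SAP 2.3.1:
- Limit the Simon sentence with 80% power and one-sided 10% to Cohort 1.
- For Cohorts 2 and 3, state one-sided 0.05 in total: 0.01 at the administrative look and 0.04 at the final analysis. Make the one-sided 96% lower limit at n = 70 and n = 52 the only success rule.
- Mark the maxima of 56 and 34 and the counts 5/56 and 6/34 as superseded and not used for any decision.
- Name the interval method and the minimum count it implies. If exact: 8/70 and 10/52, with power restated as 84% and 87%. If score: 7/70 and 9/52, with the exact type I errors of 6.0% and 7.1% disclosed.

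Elsewhere, change the all-cohort Simon statements in SAP 1, SAP 2.3 and Protocol 5.1 to Cohorts 1 and 4, and give one amendment number for the change.

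The cost is SAP wording and one protocol sentence, with no new patients or data. The choice of method should be fixed before the response counts are known: exact limits give up the stated 90% power, and score limits give up strict control at 0.04.
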